**Analysis of the clinical impact of CMV DNAemia will be performed by evaluation of:**

- Time to engraftment
- Overall mortality

The analysis will be performed comparing the clinical impact of CMV DNAemia as described before, in relation to time of CMV DNAemia initiation in the following groups:

- Patients with DNAemia before engraftment vs after engraftment
- Patients with DNAemia before engraftment and before HSC infusion vs patients with DNAemia before engraftment after HCS infusion
- Comparison of time of initiation of CMV DNAemia from day -7 to HCS infusion on a weekly basis until engraftment.

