## Objectives

**1. Assess the incidence of pre-engraftment CMV DNAemia using highly sensitive real-time PCR assays in allo-HSCT**

**2. Evaluate its impact of pre-engraftment CMV DNAemia on the time to engraftment, overall mortality, and non-relapse mortality.**

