### **Hypothesis**

**Very early episodes of CMV DNAemia have no impact on the occurrence of engraftment, overall mortality and non-relapse mortality.**

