## Statistical Plans

**Non-parametric and semi-parametric analyses.** The probabilities of CMV DNAemia, CMV DNAemia requiring pre-emptive therapy, CMV-D, NRM and relapse will be estimated by the cumulative incidence method (marginal probability).

Competing events will be defined as follows; in the case of relapse, the competing event was NRM without the occurrence of the disease. For CMV DNAemia, CMV DNAemia requiring pre-emptive therapy, CMV-D and GVHD the competing event will be relapse or death without the event. For NRM the competing event will be relapse.

The assumption of proportional hazards over time will be tested for all explanatory covariates using a time-dependent covariate. CMV DNAemia, CMV DNAemia requiring pre-emptive therapy and CMV-D will be treated as time-dependent co-variates.

If time-dependent covariates are to be included in the final model multivariate analyses of mortality the analysis will be performed by Cox proportional hazards regression model, with inclusion of those variables with a P value less than 0.1 in the prior univariate testing.

If either, early or late CMV DNAemia (included individually as time-dependent covariates) are found to have an impact on OS in the univariate analysis, semi-landmark plot will be constructed to illustrate visually the effect.

Statistical analysis of the clinical impact of CMV DNAemia at different periods of time before engraftment will be performed as described previously for early or late CMV DNAemia

All statistical analyses will be performed using SPSS version 20 (SPSS, Chicago, IL) and R version 2.12.2 (The CRAN project) with the packages survival v2.36-10, Design 2.3-0, prolim v1.2.1 and cmprsk v2.2-221.

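### Comparing time to engraftment between DNAemia 'before' and 'after' engraftment lets the outcome define the groups, so the 'before' group engrafts later even when DNAemia has no effect

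*Combined protocol and SAP*

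**What the plan says.** Objective 2 is to "Evaluate its impact of pre-engraftment CMV DNAemia on the time to engraftment, overall mortality, and non-relapse mortality". The Hypothesis is that "Very early episodes of CMV DNAemia have no impact on the occurrence of engraftment, overall mortality and non-relapse mortality". Engraftment is the first outcome in both: as a time in the objective, as an occurrence in the hypothesis.

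The section on the clinical impact of CMV DNAemia lists two outcomes, time to engraftment and overall mortality, and says that this impact will be compared in three groupings:

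1. "Patients with DNAemia before engraftment vs after engraftment"
2. "Patients with DNAemia before engraftment and before HSC infusion vs patients with DNAemia before engraftment after HCS infusion"
3. "Comparison of time of initiation of CMV DNAemia from day -7 to HCS infusion on a weekly basis until engraftment"

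Statistical Plans adds that "CMV DNAemia, CMV DNAemia requiring pre-emptive therapy and CMV-D will be treated as time-dependent co-variates". That sentence is not restricted to one outcome. The multivariable Cox model is named for mortality, and the early/late method is described for the case where "early or late CMV DNAemia (included individually as time-dependent covariates) are found to have an impact on OS in the univariate analysis". For the periods before engraftment it says: "Statistical analysis of the clinical impact of CMV DNAemia at different periods of time before engraftment will be performed as described previously". The section gives no estimator, competing event or model for engraftment.

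**The concern.** A group defined by whether DNAemia came before engraftment cannot be formed until engraftment has been observed. Every extra week without engraftment gives another PCR at which the patient can enter the 'before' group, so slow engraftment leads to membership rather than following from it.

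The contrast fails for occurrence of engraftment too. Everyone in 'after' has engrafted by definition, and any patient with DNAemia who never engrafts can only be in 'before'.

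Groupings 2 and 3 have the same fault if run on fixed groups, because a later onset that is still 'before engraftment' requires the patient to have remained un-engrafted until then.

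At stake is the first-listed outcome. Background and Rationale ties the timing of prophylaxis to the clinical impact of very early episodes, so a delay produced by the grouping would bear directly on that question.

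**Working it through.** **Inputs from the document.** N = 878 (title page). PCR is weekly from day -7 to at least day +100 (inclusion criteria). In the earlier single-center series, DNAemia began before engraftment in 38/197 = 19.3% (stated as 19%) and before infusion in 9/197 = 4.6% (Background and Rationale). At 19.3%, about 878 × 38/197 = 169 patients would be in 'before'.

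**Assumed, because the document is silent.** Lognormal engraftment times with the medians and SDs shown below; a constant onset hazard after infusion; the choice of test; two-sided 5%; no deaths. DNAemia and engraftment are generated independently, so any difference found is false.

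**Direction, by hand.** Among patients not positive before infusion, the chance of turning positive before engraftment is (38 − 9)/(197 − 9) = 29/188 = 15.4%. For engraftment at day 16 there are two post-infusion PCRs before it (days 7 and 14), so the chance per PCR is 1 − √(1 − 0.154) = 8.0%. The chance of post-infusion 'before' DNAemia then depends on engraftment day alone:

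- day 12 (one PCR): 8.0%
- day 16 (two PCRs): 15.4%
- day 24 (three PCRs): 1 − 0.920³ = 22.2%

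The chance of being in 'before' rises with engraftment time T, so the mean of T in that group exceeds the overall mean by Cov(T, w(T))/E[w(T)] > 0, where w(T) is that chance. The chance of 'after' falls with T, which widens the gap. In grouping 2, pre-infusion onset does not depend on T but post-infusion onset does, so the bias is milder and in the same direction.

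**Size, before vs after (1,000 null trials per row, weekly PCR).**

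| Engraftment median / SD (days) | Mann-Whitney rejects | Log-rank rejects | Spurious mean delay (days) | Time-dependent covariate, all 878, rejects |
|---|---|---|---|---|
| 16 / 2 | 27.0% | 19.9% | 0.26 | 4.0% |
| 16 / 3 | 70.2% | 61.4% | 0.68 | 5.5% |
| 17 / 5 | 95.5% | 91.9% | 1.69 | 4.6% |
| 18 / 6 | 98.4% | 97.8% | 2.29 | 3.5% |
| 20 / 8 | 99.6% | 99.6% | 3.53 | 4.4% |

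The simulation standard error near 5% is √(0.05 × 0.95/1000) = 0.7 points.

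**Variations (false rejection, same five cases in order).**

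| Variation | 16/2 | 16/3 | 17/5 | 18/6 | 20/8 |
|---|---|---|---|---|---|
| Onset detected continuously, Mann-Whitney | 25% | 49% | 81% | 91% | 97% |
| 'After' group cut from about 380–480 to 100 | 17% | 43% | 72% | 82% | 93% |
| Grouping 2, if run on fixed groups | 10% | 24% | 41% | 48% | 56% |
| Grouping 3, if run on fixed groups (Kruskal-Wallis) | 28% | 92% | 100% | 100% | 100% |

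A second set of ten scenarios (median 16 or 20 days, log-scale SD 0.15 to 0.4, 400 trials each) gave later engraftment in 'before' every time. The fixed-group Cox hazard ratio was 0.64 to 0.87 where the truth is 1. With the time-dependent covariate it was 1.00 to 1.01, with 3.7% to 6.0% rejection.

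**Occurrence.** Take an assumed 2% graft failure, independent of DNAemia, with failures observed to day 28 (four post-infusion PCRs). The chance that a failure has DNAemia is 1 − (188/197) × 0.920⁴ = 31.7%. Failure in 'before' is then 0.02 × 0.317/(0.02 × 0.317 + 0.98 × 0.193) = 3.2%, against 0% in 'after'. Simulating 1% to 3% failure, with observation to day 28 or 42, gave 1.4% to 6.7% against 0%, and Fisher's test rejected in 42% to 100% of trials.

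**The case against.** The best defence is the general statement that DNAemia is time-dependent. It does not save the before/after contrast: in a model for engraftment, post-engraftment DNAemia is zero for every patient still at risk, so the 'after' effect cannot be estimated.

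A second defence is that the groupings may have been meant mainly for mortality. The earlier series, as summarised in the background, reports pre- versus post-engraftment comparisons for several outcomes but none for time to engraftment. However, the current text puts time to engraftment first among the outcomes to be compared across these groups, and that is its literal reading.

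Four points stand:

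- Groupings 2 and 3 can be read as assigned to time-dependent modelling. The method referred back to is described for OS only, so for them this is a matter to clarify, and the rates above apply only if fixed groups are used.
- Occurrence of engraftment appears only in the hypothesis. No test of it is stated, so that calculation is conditional.
- The sizes rest on assumed distributions. In real data, confounding could add to or offset the bias.
- A landmark at a fixed day, among patients not yet engrafted, would also be valid, and before/after groups may be kept for description.

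**Conclusion.** The before/after contrast is wrong as written for time to engraftment and must be changed. With DNAemia and engraftment independent, the 'before' group engrafts later because of how it is formed. That holds whatever the spread of engraftment times. The size does not: across the cases tried, the delay runs from about a quarter of a day to about 3.5 days, and false rejection by Mann-Whitney from 27% to 99.6% (17% to 93% with a small 'after' group). Even the mildest case is more than three times the nominal 5%. The error favours a finding of delayed engraftment and so works against the stated hypothesis. The criticism does not extend to mortality, where early and late DNAemia are already planned as time-dependent covariates for OS.

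**What to change.** For time to and occurrence of engraftment, drop the before/after contrast and do not run groupings 2 and 3 on fixed groups. Replace them with one pre-specified analysis:

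- a cause-specific Cox model from day 0 in all eligible patients, including those who never develop DNAemia;
- DNAemia as a time-dependent covariate, switching from 0 to 1 at the first positive PCR, with no DNAemia so far as the reference;
- pre-infusion DNAemia as a baseline level, and post-infusion onset, by week if wanted, as time-dependent levels, which answers groupings 2 and 3;
- death without engraftment as a competing event, and patients who never engraft kept at risk to a pre-stated horizon;
- the definition of engraftment stated.

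Under the null, the version with pre- and post-infusion levels rejected in 3.6% to 5.8% of trials and the by-week version in 4.0% to 7.2% (500 trials each; standard error about 1.0 point). The by-week levels should therefore be few and secondary.

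Keep the before/after contrast for mortality only, with both as time-dependent covariates, and state in Statistical Plans that the time-dependent method covers engraftment as well as OS.

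The cost is SAP wording and a counting-process data layout. Longitudinal PCR results are already to be reported by the centers. Engraftment dates are not listed by name, but the plan's own endpoint needs them.

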NCT number	NAV-CMV-2019
Date	May, 2018
Study Title:	Pre-engraftment Cytomegalovirus DNAemia in allogeneic hematopoietic stem cell transplant recipients: incidence, risk factors and clinical outcomes
Request Date:	
Principal Investigator Contact Information	[name]
Name:	[name]
Title:	MD, PhD
Address 1	[name]
Address 2	
City, ST, Zip	[name]
Phone/Fax:	[name]
[contact]	
Institution Contact Information	INCLIVA, Institución de Investigación Sanitaria, Hospital Clínico de Valencia
Name:	INCLIVA, Institución de Investigación Sanitaria, Hospital Clínico de Valencia
Address 1	[name]
Address 2	
City, ST, Zip	[name]
Phone/Fax:	[name]
website	
Number of Subjects: 878	

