## Background and Rationale

Cytomegalovirus DNAemia occurs frequently in allogeneic hematopoietic stem cell transplant (allo-HSCT) recipients [1]. Both high-level and persistent virus DNAemia are known risk factors for CMV end-organ disease and perhaps non-relapse mortality [2]. CMV DNAemia is usually documented after engraftment, but it may occur before. The virological features and clinical consequences of these latter early-onset episodes remain largely unexplored. The U.S. Food and Drug Administration (FDA) has recently approved letermovir for prophylaxis of CMV infection and disease in adult CMV-seropositive allo-HSCT recipients (PREVYMIS™, Merck & Co., New Jersey, USA). In accordance with the design of the phase III, double-blind trial [3] the drug may be administered as early as the day of transplant and no later than 28 days post-transplant. Nevertheless, the timing of drug inception should be contingent on the clinical impact of very early episodes of CMV DNAemia. In a recent work from our group (single-center study) [4] we found that a total 38 out of the 197 patients in our series developed CMV DNAemia before engraftment (cumulative incidence, 19%; 95% CI, 10-30.3%). Nine episodes of CMV DNAemia were detected prior to the time of donor progenitor cell infusion. A greater number of post-engraftment episodes required preemptive antiviral therapy compared with pre-engraftment episodes (62.5% vs 44.7%;  $P=0.05$ ). The cellular content of the donor progenitor cell infusion and transplant characteristics of patients did not differ between patients with pre- or post-engraftment CMV DNAemia. The cumulative incidence of overall mortality by days 100 and 365, aGVHD by day 100 and relapse by day 365 were not significantly different between patients with pre-engraftment or post-engraftment CMV DNAemia. Our study was limited by the retrospective and single-center design and the scarce number of pre-engraftment CMV DNAemia episodes included; therefore, the results may not be extrapolated to other transplantation centers or patient cohorts. Further retrospective and prospective studies are thus required to validate the data presented herein.

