**Inclusion criteria include:**

- Recipients >18 years old
- CMV seropositive recipients and/or donors
- DNA load monitoring by real-time PCR starting from day -7 and conducted on a weekly CMV basis (0, +7, +14,...) at least until day +100
- First allo-HSCT
- T-cell replete allograft

Essential variables which include patients, donor and transplant's characteristics as well as post-transplant outcome will be retrieved from MED-A of PROMISE EBMT database.

Specific CMV data (including one-year longitudinal PCR results, date of onset and type of pre-emptive antiviral therapy as well as CMV disease data) will be retrospectively reported by each participating center.

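### The weekly onset windows are tested one at a time, with no test of whether risk differs between weeks and no multiplicity control, so differences in significance can be mistaken for differences in risk

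*Combined protocol and SAP*

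**What the plan says.** The section on the clinical impact of CMV DNAemia names time to engraftment and overall mortality as outcomes and lists three comparisons by time of onset: before versus after engraftment; within pre-engraftment DNAemia, before versus after infusion; and a "Comparison of time of initiation of CMV DNAemia from day -7 to HCS infusion on a weekly basis until engraftment".

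Statistical Plans gives the method for the third in one sentence: the analysis of clinical impact "at different periods of time before engraftment will be performed as described previously for early or late CMV DNAemia". For early and late DNAemia, the text above that sentence enters each singly as a time-dependent covariate and, if either affects overall survival in univariate analysis, draws a semi-landmark plot. The only P-value threshold anywhere is P<0.1, for carrying variables into the multivariable Cox model.

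Neither section states the number of weekly windows, the reference group, a significance level, a between-week test or a multiplicity rule. The Background explains why timing matters: "the timing of drug inception should be contingent on the clinical impact of very early episodes of CMV DNAemia".

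**The concern.** The weekly analysis asks whether the effect of DNAemia depends on when it starts. Separate tests of each week do not answer that. One significant week beside one non-significant week is no evidence that the two differ; that takes a direct comparison.

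Two errors follow. If DNAemia has no effect, which is the study's own hypothesis, several unadjusted tests give several chances of a falsely significant week. If it has the same effect in every week, small weekly groups will often make some weeks significant and others not, and the pattern will look like a timing effect. Either could colour the answer to the question that the Background raises about very early episodes.

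**Working it through.** **Inputs from the documents**
- Size: "Number of Subjects: 878". No power, effect size or event count goes with it, so there is no design calculation to reproduce.
- Incidence in the earlier single-centre series: "38 out of the 197 patients in our series developed CMV DNAemia before engraftment (cumulative incidence, 19%; 95% CI, 10-30.3"%. Check: 38/197 = 19.3%, which agrees. Applied to 878: 0.19 × 878 = 167 cases, with 88 to 266 at the confidence limits.
- Split at infusion: "Nine episodes of CMV DNAemia were detected prior to the time of donor progenitor cell infusion". Hence 878 × 9/197 = 40 cases before infusion and 878 × 29/197 = 129 after it.
- PCR schedule: from day -7, "conducted on a weekly CMV basis (0, +7, +14,...) at least until day +100".

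**Assumptions, because the documents are silent**
- Number of weeks k: 3 to 6, mainly 4 or 5. No time to engraftment is given.
- Level: two-sided 0.05.
- Deaths by day 365: 35%, with 20-45% as the range.
- Common hazard ratio: 1.2 to 2.5.
- Cases spread evenly over the weeks. With k = 4 that is 167/4 ≈ 42 patients per week and, under no effect, 42 × 0.35 ≈ 15 deaths.

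**Step 1: no effect in any week.** Treating the k tests as independent, P(any significant week) = 1 − 0.95^k and P(any falsely harmful week) = 1 − 0.975^k.

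| k | Any direction | Harmful only |
|---|---|---|
| 3 | 14.3% | 7.3% |
| 4 | 18.5% | 9.6% |
| 5 | 22.6% | 11.9% |
| 6 | 26.5% | 14.1% |

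Simulation of 878 patients (4,000 runs) gave 18-20% (k = 4) and 23% (k = 5) for any direction. For harmful only it gave 13-14% and 16-17%, above the formula because the score test is skewed in small groups. If P<0.1 were used as the criterion, the any-direction rate would be 1 − 0.9^4 = 34.4% (k = 4) or 1 − 0.9^5 = 41.0% (k = 5). The harmful-only rate would be 18.5% or 22.6% by formula, and 22-23% or 27-28% by simulation.

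**Step 2: the same hazard ratio in every week.** Schoenfeld's formula gives power per week = Φ(ln HR × √(D q (1 − q)) − 1.96). With D = 878 × 0.35 = 307 deaths and q = 0.19/4 = 0.0475, √(307.3 × 0.0475 × 0.9525) = 3.73. With per-week power p, the chance that some but not all of four weeks are significant is 1 − p^4 − (1 − p)^4.

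| HR | p | Mixed, formula | Mixed, simulation* |
|---|---|---|---|
| 1.2 | 0.10 | 34% | 43% |
| 1.5 | 0.33 | 78% | 83% |
| 2.0 | 0.73 | 70% | 43% |
| 2.5 | 0.93 | 26% | 6% |

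*2,000 runs, each week against patients without early DNAemia. Against all other patients, the simulated rate at HR 1.5 is 82%.

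For k = 4 the mixed rate cannot exceed 1 − 2 × 0.5^4 = 87.5%, so HR 1.5 with 35% mortality lies near the peak. Over the whole grid (incidence 10-30.3%, mortality 20-45%, HR 1.2-2.5, k = 4 or 5) it runs from about 1% to 94%.

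**Step 3: a joint test instead.** In the same simulations one heterogeneity test on k − 1 degrees of freedom declared a false difference between weeks in about 4-7% of studies, both under no effect and under a common HR. A pooled test of early DNAemia had about 87% power at HR 1.5 and 35% mortality, against 32-45% for one week (k = 4).

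**Limits.** The simulations fix onset at baseline, which simplifies a time-dependent covariate, and they cover deaths only, not time to engraftment.

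**The case against.** The strongest reply is that the method may be wider than this reading allows. The third item is itself called a comparison, the reference back could take in the multivariable Cox model, and the words on single entry occur in a sentence about when to draw a plot. That is fair: the plan does not rule out a between-week test. But it provides no method for one, and if one is intended it still has to be written down.

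A reader might also infer more than the documents support:
- **That no analysis addresses timing.** The before/after-engraftment and before/after-infusion comparisons are direct timing contrasts. The gap is confined to the weekly analysis.
- **That a spuriously harmful week turns up in about one null study in five.** At two-sided 0.05 that is the rate for a significant week in either direction. Harmful weeks alone reach about one in five only if the P<0.1 model-entry threshold serves as the test.
- **That about four studies in five would give mixed verdicts whenever the weeks share a risk.** This holds near HR 1.5 with 35% mortality and falls well below that at smaller or larger hazard ratios.
- **That one significant week would set a date for starting prophylaxis.** The Background links timing to very early episodes in general, but no section says that a single week will decide anything.

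**Conclusion.** The concern holds in limited form. Followed as written, the plan tests the onset weeks singly by univariate P value, with no test between them and no multiplicity control, so it can present a difference in significance as a difference in risk.

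For any number of weeks from 3 to 6, the chance of at least one falsely significant week is about 14-27% (about 19-23% for 4 or 5 weeks), against a nominal 5%. For a falsely harmful week it is about 10-17% with 4 or 5 weeks. These figures need only the number of weeks, the 0.05 level and near-independence of the tests. The mixed-verdict rate depends far more on assumptions: with four weeks and 35% mortality it is about 80% at HR 1.5, 34-43% at HR 1.2 and 6-26% at HR 2.5. It should be quoted only with those conditions.

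The plan should be changed, because the repair is cheap and the question is one of the study's listed comparisons.

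**What to change.** In Statistical Plans, replace the sentence that refers the pre-engraftment periods back to the earlier method with the following:

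1. State the weekly windows, the reference group and the significance level.
2. For each outcome, fit one time-dependent Cox model with pre-engraftment DNAemia (yes/no) plus onset week.
3. Base any claim that timing matters on one prespecified joint test of heterogeneity between onset weeks.
4. Give an ordered onset-day trend as a supporting analysis. It should not be the sole arbiter, because a linear term can miss a step at infusion.
5. Keep the before/after-infusion contrast already listed.
6. Report weekly hazard ratios with 95% confidence intervals as description, and single out no week on its own P value.

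No new data are needed, since the weekly PCR results are already to be collected. The cost is some power: an isolated one-week effect is harder to detect, and so is a smooth trend. As an illustration, let the HR fall log-linearly from 2 to 1 over four weeks of about 42 patients with 35% reference mortality. Expected deaths d are 24.1, 20.7, 17.5 and 14.6; log HRs are 0.693, 0.462, 0.231 and 0, with death-weighted mean 0.394. The noncentrality Σd(log HR − mean)² is 5.0, which gives about 44% power on 3 degrees of freedom, against about 61% for a one-degree-of-freedom trend. A non-significant heterogeneity test should therefore be reported with its intervals and not as proof that timing is irrelevant.
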